### 10.3 Prohibited therapies

Any COVID-19 vaccine in the 28 days before OR after any dose of enadenotucirev, unless the vaccine is known to not be based on an adenoviral vector.

- COVID-19 vaccines known to not be based on an adenoviral vector (e.g., the mRNA-1273 SARS-CoV-2 [Moderna Therapeutics] and BNT162b2 [BioNTech/Pfizer] mRNA COVID-19 vaccines or other non-adenoviral vaccines) are excluded in the 7 days before OR after any dose of enadenotucirev

Any other vaccine, in the 7 days before OR after any dose of enadenotucirev.

Medications inducing immune suppression (e.g. systemic corticosteroids or other immunosuppressive medications) in the 14 days after the last dose of enadenotucirev unless they are:

- Required as part of emergency therapy
- Required for the treatment of adverse events
- Used as an inhaled agent for bronchospasm or COPD

Anti-viral agents e.g. ribavirin, adefovir, lamivudine or cidofovir in the 7 days after each trial treatment; or PEG-IFN in the 14 days after each dose of trial treatment and only then if the benefit of their use will outweigh the possible risks.

Any systemic cancer therapy other than capecitabine and any local therapy to the primary tumour or its metastases during trial treatment.

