**5.3.2 Evaluation schedule B*****Pre-Dose***

- Adverse events and DLTs since the previous assessment
- New or changes to existing medications
- Physical examination of major body systems
- Vital sign measurements: systolic / diastolic blood pressure (BP), pulse rate, respiratory rate and temperature
- Weight
- ECOG performance status

It is recommended that subjects also receive antipyretic prophylaxis, steroid prophylaxis and hydration at the time of each injection of enadenotucirev (See section 8.3). The recommended regime is:

- 1 hour prior to administration
  - IV hydrocortisone 100mg
  - PO Paracetamol 1000mg

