**Subsequent doses:**

On all subsequent doses the patient's vital signs must be monitored at the following time points:

- Immediately after the end of the infusion
- 30 minutes ( $\pm 5$  minutes) post end of infusion
- 1 hour ( $\pm 15$  minutes) post end of infusion
- 3 hour ( $\pm 15$  minutes) post end of infusion

They will also receive a further dose of Hydrocortisone (IV) and paracetamol (PO) at 3 hours [See section 8.3]. If they are clinically well and vital signs are normal they can be discharged. If not improving consider admission for further active management.

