### **8.3 Management of drug administration**

#### Enadenotucirev

Enadenotucirev is a live replicating oncolytic adenovirus; it is considered a BioSafety Level 1 (BSL-1) infectious substance. Appropriate precautions should be followed for a BSL-1 substance, as per section 8.4 and local site policy.

Subjects must receive antipyretic prophylaxis, steroid prophylaxis and hydration at the time of each injection of enadenotucirev. The recommended regime is:

- 1 hour prior to administration
  - IV hydrocortisone 100mg
  - PO Paracetamol 1000mg
- 3 hours following administration
  - IV hydrocortisone 100mg
  - PO Paracetamol 1000mg

It is also strongly recommended that all patients have loperamide prescribed prior to commencement of treatment, in case of development of diarrhoea (see section 9.3).

Patients should also be given a prescription for oral paracetamol 1000mg four times daily to be taken in the 24 hours after receiving enadenotucirev.

The enadenotucirev infusion solution should be made up as per the administration protocol. Once diluted in the infusion bag/syringe it must be administered to the patient within 6 hours of preparation. The diluted solution is stable at room temperature (20-26°C) for up to 1 hour. If not administered within 1 hour it can be stored at +2°C to 8°C for no longer than 6 hours until administration. The full infusion volume must be administered over a 15 minute (+/- 5minutes) period for all dosing groups.

**NOTE:** At the time of administration, the extension set used to administer enadenotucirev can be primed with saline. At the end of infusion, the line will also need to be flushed with saline. This will ensure that all 30 mL of diluted enadenotucirev are administered to the patient.

The patient should be observed after administration as per post-dosing assessments detailed in section 5.3. N.B. serious infusion reactions have been observed in previous trials of enadenotucirev, appearing to reflect cytokine responses to treatment. In the event of a serious infusion reaction the infusion should be discontinued and the patient monitored and treated as per standard local protocol for management of cytokine release syndrome. Further guidance on managing toxicities is given in section 9.2.

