## 10 OTHER TREATMENTS (NON-IMPS)

### 10.1 Support medication

Local anti-emetic and anti-diarrheal policy may be followed. Medications for the standard management of symptoms or supportive care for cancer or for the management of the effects of enadenotucirev may be administered at the Investigator's discretion; unless they are excluded concomitant medications.

**Antipyretic prophylaxis:** Subjects must receive antipyretic prophylaxis and hydration at the time of each injection of enadenotucirev (as per section 8.3) unless clinically excluded (e.g. allergic to paracetamol, when alternatives should be used such as NSAIDS).

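### The protocol gives conflicting instructions on steroid prophylaxis with enadenotucirev, chiefly at the first infusion, and prohibits one administration that it also directs

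*Protocol*

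**What the plan says.** Five places in the protocol deal with steroid cover around enadenotucirev.

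- **Section 8.3** makes it compulsory: "Subjects must receive antipyretic prophylaxis, steroid prophylaxis and hydration at the time of each injection of enadenotucirev". The regime that follows, which 8.3 labels as recommended, is IV hydrocortisone with oral paracetamol one hour before the infusion and again "3 hours following administration".
- **Section 5.3.2 (schedule B)** is weaker: "It is recommended that subjects also receive antipyretic prophylaxis, steroid prophylaxis and hydration at the time of each injection of enadenotucirev". It lists only the administration one hour beforehand. Section 5.3.1 (schedule A) has no premedication text.
- **Section 5.4**, under subsequent doses, states: "They will also receive a further dose of Hydrocortisone (IV) and paracetamol (PO) at 3 hours". Its separate list for the first dose contains vital-sign checks only.
- **Section 10.1** states: "Subjects must receive antipyretic prophylaxis and hydration at the time of each injection of enadenotucirev (as per section 8.3) unless clinically excluded". It does not name the steroid.
- **Section 10.3** prohibits "Medications inducing immune suppression (e.g. systemic corticosteroids or other immunosuppressive medications) in the 14 days after the last dose of enadenotucirev unless they are" emergency therapy, "Required for the treatment of adverse events", or an inhaled agent for bronchospasm or COPD. It has no exception for prophylaxis given under the protocol.

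**The concern.** A site that works from the visit instructions in section 5 can arrive at different steroid cover from a site that works from 8.3. The difference is widest at the first infusion, where neither the pre-dose nor the post-dose instructions mention a steroid. Section 9.3 says that infusion reactions are more common with the first infusion, and section 1.2 says that the cytokine response weakens with later doses.

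This reaches the primary endpoint. Section 9.1 counts cytokine release syndrome of grade 3 or above as a DLT. The toxicity model in SAP section 6.2.1 relates DLTs to the treatment schedule, with weights for follow-up time and dose received, and has no term for premedication. If cover varies, the DLT rate estimated for a schedule is an average over more than one regimen. Separately, a patient treated exactly as 8.3 and 5.4 direct would breach 10.3 after the final infusion.

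**Working it through.** The plan states no figure on this point, so there is none to reproduce. The check sets the sections side by side and counts hydrocortisone administrations.

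**Inputs.** Infusions per schedule come from the table in 8.2: 3; 3 + 3 = 6; 3 + 3 = 6; 3 + 2 + 3 = 8. Write n for this number. Two administrations per infusion (1 hour before, 3 hours after) come from 8.3. The tables in 5.3 assign schedule A to dosing days 1 and 3 of loading and maintenance and to both concurrent doses, and schedule B to dosing day 2.

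**Step 1: what each text yields if followed alone.**

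| Text followed | Sch. 1 | Sch. 2 | Sch. 3 | Sch. 4 |
|---|---|---|---|---|
| Infusions, n | 3 | 6 | 6 | 8 |
| 8.3 in full, 2n | 6 | 12 | 12 | 16 |
| 8.3, but no 3-hour administration after the first infusion (5.4 taken literally), 2n − 1 | 5 | 11 | 11 | 15 |
| Pre-dose part only (list in 5.3.2), n | 3 | 6 | 6 | 8 |
| Infusions whose pre-dose instructions (schedule A) name no steroid | 2 | 2 + 2 = 4 | 2 + 2 = 4 | 2 + 2 + 2 = 6 |

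The first infusion is a schedule A visit on every dose schedule.

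**Step 2: what falls in the 14-day window of 10.3.** The result is the same for every permitted pattern of three non-consecutive days within seven.

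- *Last dose read as the final dose.* Only the 3-hour administration after the final infusion comes later than that dose. That is 1 of 6, 1 of 12, 1 of 12 and 1 of 16. The final infusion is always a subsequent dose, so 5.4 says without qualification that the steroid will be given, and 10.3 prohibits it.
- *Last dose read as the most recent dose.* Every administration is caught except a pre-dose one with no infusion in the preceding 14 days. On schedule 1 that is the first pre-dose administration: 6 − 1 = 5. On schedules 2 and 3 it is also the first maintenance pre-dose administration, because loading ends by day 14 and maintenance starts no earlier than day 50: 12 − 2 = 10. On schedule 4 the day 15 dose follows the last loading dose by at most 10 days, and maintenance follows day 19 by at least 31: 16 − 2 = 14.

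On neither reading does 10.3 reach the administration before the first infusion.

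**Step 3: which reading is natural.** Within 10.3, vaccines are tied to any dose and antivirals to each treatment. The change to the last dose for immunosuppressants therefore points to the final dose. Usage is not uniform, however: 10.4 bars vaccination for a week after the last dose where 10.3 says any dose. The term needs a definition.

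**The case against.** The strongest defence is that 8.3 is the administration section, says the prophylaxis is compulsory, and is where the other texts point. Sections 5.3.2, 5.4 and 10.1 all cross-refer to it. The sentence in 5.3.2 covers each injection, so its place under schedule B misleads but does not confine it to dosing day 2. Section 5.4 speaks of a further dose, which presupposes an earlier one. The paragraph in 10.1 is about antipyretics, so it is silent on steroids and not contrary to 8.3. All of this stands, and it narrows the point.

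It does not remove it. The linked texts differ in force (compulsory against recommended) and in content (with or without the 3-hour administration). The two lists that govern the first infusion, schedule A and the first-dose list in 5.4, carry no steroid text and no pointer to 8.3 for premedication.

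A reader might infer three stronger things that the documents do not support.

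- *That 10.3 forbids the prophylaxis as a whole.* On the natural reading it catches one administration per patient, at the final infusion, where the argument about cytokine reactions is weakest.
- *That exclusion 3a also conflicts.* It concerns significant immunodeficiency at entry, not premedication at an infusion.
- *That the effect on escalation can be quantified.* Under the SAP priors, with full weights, the posterior probability that the DLT rate at schedule 2 exceeds 0.35 is 0.077 after no DLT in two patients on schedule 1, and 0.385 after one, which is above the 0.35 safety limit. That is the effect of any DLT from any cause. Nothing in the documents says how often steroid cover would decide whether one occurs.

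**Conclusion.** The contradiction is real and should be corrected. Section 8.3 requires what 5.3.2 only recommends. The 3-hour hydrocortisone is present in 8.3, absent from 5.3.2, and in 5.4 appears for subsequent doses only. The instructions for the first infusion name no steroid. As a secondary matter, 10.3 prohibits one administration per patient that 8.3 sets out and 5.4 directs. This rests on reading the last dose as the final one; on the other reading the conflict covers 5 of 6, 10 of 12, 10 of 12 and 14 of 16.

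That cover would differ between sites is an inference from the conflicting force and the omissions in sections 5 and 8, not from the 10.3 window. A site that follows 8.3 alone may not omit the steroid. The consequence for the DLT rate is plausible, but its size cannot be stated.

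**What to change.** Reconcile 5.3.1, 5.3.2, 5.4, 8.3, 10.1 and 10.3 into one statement, cross-referenced from each of the others, of whether steroid prophylaxis is mandatory, at which doses (the first named explicitly) and at which times. Define the last dose in 10.3 and say whether protocol prophylaxis is exempt from the prohibition. The clinical team decides the content; this review takes no position on it.

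Optionally, make the premedication given at each infusion visible to the TMG at dose decisions, so that it can see whether a DLT arose with or without it. Medication changes are already collected under schedules A and B. The content of the Patient Status Update CRF is not shown, so it is not known whether this would be a new item.

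The cost is protocol wording and at most one CRF item, with no added procedure for patients.

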### 10.4 (Potential) Drug Interactions

#### Enadenotucirev

Enadenotucirev is sensitive to the effects of cidofovir and likely to be sensitive to other agents with known anti-viral effects, therefore these medications are prohibited as detailed in the previous section. Systemic cancer therapy may have an inhibitory effect on enadenotucirev, hence capecitabine should not be administered on enadenotucirev dosing days. Refer to the current Investigator Brochure for further detail.

The inflammatory reactogenicity observed with COVID-19 vaccinations may overlap with the acute cytokine driven symptoms observed shortly after dosing with EnAd-based IMP (including chills, pyrexia and potential acute respiratory symptoms). To mitigate against this risk patients in this trial should not be treated with EnAd-based IMP within one week of receiving any vaccination (either first or second dose). Additionally, patients should not receive a vaccination within one week of their last dose of EnAd-based IMP.

In addition, several COVID-19 vaccines based on adenoviruses have now been approved. Due to the specific potential for overlap in immune responses between adenovirus-based vaccines and EnAd-based IMP, a default requirement that patients do not receive a COVID-19 vaccine in the 28 days before or after any dose of EnAd-based IMP has been added to the protocol. If the COVID-19 vaccine is known to be non-adenoviral (e.g. mRNA vaccines), then a 7-day exclusion before or after any dose of EnAd-based IMP is required.

**Capecitabine - advisory**

Capecitabine interacts with several medications and investigators should refer to the SPC for full guidance. For ease of reference the following are the main interactions:

- Coumarin-derivative anticoagulants e.g. warfarin- more frequent is monitoring required when administered with capecitabine due to altered coagulation parameters. Effects may occur up to several months after initiating capecitabine therapy.
- Phenytoin- increased phenytoin plasma concentrations resulting in symptoms of phenytoin intoxication in single cases have been reported during concomitant use of capecitabine. Patients should be regularly monitored for increased phenytoin plasma concentrations.
- Folinic/ folic acid has an effect on the pharmacodynamics of capecitabine and its toxicity may be enhanced.
- Capecitabine must not be administered concomitantly with sorivudine or its chemically related analogues (e.g. brivudine)
- Aluminium hydroxide or magnesium hydroxide containing antacids – cause a small increase in plasma concentrations of capecitabine and its metabolite 5DFCR (5'-deoxy-5-fluorocytidine)
- Cytochrome p450 down regulation by capecitabine may affect the following class of drugs – angiotensin II blockers (losartan, valsartan); oral hypoglycaemic agents (glipizide, tolbutamide, rosiglitazone); NSAIDS (indomethacin, celecoxib, diclofenac, ibuprofen)
- Concomitant use of allopurinol with capecitabine should be avoided

## 11 DRUG MANAGEMENT

### 11.1 Drug supplies

Enadenotucirev will be supplied free of charge to the local hospital pharmacies. Enadenotucirev is provided as single use vials containing  $1.4 \times 10^{12}$  viral particles in 0.7mL aliquots in 2mL type 1 borosilicate glass vial with a butyl stopper and an aluminium crimp seal. Each vial of enadenotucirev is issued in a plastic tamper-evident container.

Capecitabine as a tablet for oral use should be supplied from trial site's own stock and funded locally.

All supportive medication is to be sourced and funded locally.

### 11.2 Drug ordering

Initial supplies of enadenotucirev are dispatched by Fisher Bioservices, on behalf of Psioxus after Psioxus have been informed by OCTO that all approvals are in place and the site is open to recruitment. Subsequent supplies should be ordered from OCTO by site pharmacy using the drug request form provided. Email the completed form to [[contact]](mailto:[contact]).

The Principal Investigator and Pharmacy are responsible for liaising to ensure that adequate stock levels are held as necessary to supply the recruited patients.

If a vial of enadenotucirev is accidentally destroyed, i.e. by dropping the vial or through contamination, the pharmacist can contact [[contact]](mailto:[contact]) for replacement patient supplies and submit a drug request form if required.

### 11.3 IMP Receipt

Sites should contact the trials office via email ([[contact]](mailto:[contact])) to confirm receipt of enadenotucirev and complete confirmation of receipt as per the supplier's instructions.

If supplies are damaged on arrival contact the Trial Office. Damaged supplies should be destroyed on site as per local policy and a drug destruction form completed. See section 11.9 – drug destruction.

### 11.4 Handling and storage

Enadenotucirev should remain frozen solid at all times during transit and storage. The enadenotucirev vial should be kept inside a secondary container and should be quickly transferred to the designated, controlled-access freezer for storage below -80°C (with normal  $\pm 10^\circ\text{C}$  tolerance).

The temperature will be monitored during transport and site storage and logs will need to be reviewed at site before the virus is dispensed. Temperature excursions should be reviewed and the trials office notified. The virus should be quarantined until a decision has been made that it is still fit for purpose or that it must be destroyed.

Enadenotucirev is a live replicating oncolytic adenovirus, it is considered a BioSafety Level 1 (BSL-1) infectious substance. Appropriate precautions should be followed for a BSL-1 substance, as per section 8.4 and local site policy.

## 11.5 Labelling

### Enadenotucirev

Enadenotucirev vials supplied to sites will have been labelled for clinical trial use as per the requirements of Eudralex Volume 4: Annex 13 'Investigational Medicinal Products' of the European Union guide to Good Manufacturing Practice (GMP).

Site pharmacies are permitted to add additional labels to the IMP at site as per standard local procedures (e.g. addition of site and patient identifiers) providing the original label is not obscured.

### Capecitabine

Labelling will be as per local practice.

## 11.6 Dosing dispensing

Enadenotucirev is a live replicating oncolytic adenovirus, it is considered a BioSafety Level 1 (BSL-1) infectious substance. Appropriate precautions should be followed for a BSL-1 substance, as per section 8.4 and local site policy.

The enadenotucirev infusion solution should be made up as per the administration protocol. Once diluted in the infusion bag/syringe it **must be administered to the patient within 6 hours of preparation**. The diluted solution is stable at room temperature (20-26°C) for up to 1 hour. If not administered within 1 hour it can be stored at +2°C to 8°C for no longer than 6 hours until administration.

## 11.7 Drug accountability

Drug accountability is the responsibility of the site pharmacist listed on the trial delegation log. Full drug accountability records must be maintained for capecitabine and enadenotucirev. Hospitals may amend the Drug Accountability Logs provided by the trial office or use their own documentation if it captures all the information requested on the Drug Accountability Logs and has been approved by the Trial Office in advance.

Copies of completed accountability logs must be supplied to the trial office on request.

## 11.8 Drug returns from patients

Site staff will collect and count patient returns of capecitabine. Returns should be reconciled against the patient diary and the reason for any discrepancy documented. Returns must be recorded in the patient's CRF and accountability log. The returns can then be disposed of according to local policy.

## 11.9 Drug destruction

### Enadenotucirev:

Used vials	Disposal at site according to local hospital policy.
Expired Virus	Disposal at site according to local hospital policy. A dated certificate of disposal should be completed and retained in the Pharmacy File and a copy emailed to the trial's office.
Virus left unused	At the end of the trial, once authorised to do so, any unused drug should be disposed of at site according to local hospital policy. A dated certificate of disposal should be completed. The original should be placed in the Pharmacy File and a copy emailed to the Trials Office.

### Capecitabine:

Patient returns will be disposed of as per local hospital policy.

## 11.10 Occupational safety

Enadenotucirev is a live replicating oncolytic adenovirus; it is considered a BioSafety Level 1 (BSL-1) infectious substance. Appropriate precautions should be followed for a BSL-1 substance, as per section 8.4 and local site policy.

## 12 RADIOTHERAPY (AND CHEMORADIOThERAPY)

Patients registered for the trial will receive standard chemoradiation treatment which consists of Capecitabine 900mg/m^2 orally twice a day in equal doses (Mon-Fri) on the days of radiotherapy for 25 daily treatments. The radiotherapy protocol mandates the use of intravenous contrast CT simulation with minimum 3 mm CT slices. Patients are immobilised supine with customised pelvic immobilization equipment, with a comfortably full bladder.

50Gy in 25 fractions will be delivered to the primary tumour and macroscopically involved lymph nodes as a simultaneous integrated boost and 45Gy in 25 fractions to the pelvis/mesorectal nodes and elective pelvic lymph nodes at risk, prescribed according to recommendations by the International Commission on Radiation Units and Measurements (ICRU-50/62), to be delivered Monday to Friday as an intensity modulated radiotherapy planned single-phase treatment. An adapted atlas will be provided to aid with radiotherapy localization (Elective Clinical Target Volumes in Anorectal Cancer: An RTOG Consensus Panel Contouring Atlas). Each case will be reviewed to ensure consistency of radiotherapy delineation and radiotherapy dose delivery as described in section 12.3. Patients are reviewed weekly during RT (as per standard of care) and prior to each administration of enadenotucirev.

Please refer to the accompanying radiotherapy trial document for details on volumes, margins, organ at risk constraints', plan optimisation and quality assurance to ensure that standard of care is consistent across the sites.

